5.4 Study Flow Chart

The Figure 2 and the Table 3 below summarize subject flow and requirements of the study.

Figure 2: Cohort 2 Flow Chart

Template: 86357 Rev. F Page 11 of 26

Clinical Investigation Plan

Table 2: Cohort 2 Data Collection tests and procedures

VISIT	BASELINE	POST- PROCEDURE (UP TO 7	6 MONTHS* (>150 DAYS)	>6 MONTHS** (> 183 DAYS)
STUDY ACTIVITY		DAYS)		
Informed Consent Process				X
Demographics/Medical History	х			
Echocardiogram		Х	X*	

^{*}If subject was alive during the visit window

5.5 Requirements for Clinical Laboratories

An echocardiography core laboratory will assess echocardiograms for residual shunt and quantification of shunts.

5.6 Study Committee

5.6.1 Publication Committee (PC)

A Publication Committee may be established to oversee study publications. Publication Committee membership may include Principal Investigators, a representative of the Sponsor and a statistician. The Publication Committee will be responsible for identifying, selecting and approving publication proposals and determining authorship according to a Publication Plan. A Publication Committee charter will define membership of the committee and outline the roles and responsibilities of the committee, as well as rules to define authorship.

6 Statistical Considerations

The following section describes the statistical methods for the clinical study and justification of the design.

6.1 Endpoints

There are five endpoints, three effectiveness endpoints and two safety endpoints. There are no hypotheses to be tested.

6.1.1 Effectiveness Endpoint 1: Technical Success

Technical success occurs when a subject is successfully implanted with a PIVSD device in the ventricular septal defect. An implant attempt occurs when the delivery system is inserted in the subject's vasculature.

6.1.1.1 Analysis Methods per Subject (Subject-Level Technical Success)

The proportion of subjects who experience technical success will be estimated.

Template: 86357 Rev. F Page 12 of 26

^{**}Since all data are retrospectively collected, informed consent occurs at 6 month or beyond the PIVSD occluder implant procedure

Clinical Investigation Plan

The 95% confidence interval for the rate of technical success will be calculated using the exact binomial method.

6.1.2 Effectiveness Endpoint 2: Acute Closure

Acute closure is defined as the absence of a residual shunt ≥3 mm, and will be assessed based on an echocardiogram obtained immediately after successful deployment and up to 7 days post-procedure.

6.1.2.1 Analysis Methods

The proportion of subjects who have acute closure post-procedure, as determined by the echocardiography core laboratory, will be estimated.

he 95% confidence interval for the rate of acute closure will be calculated using the exact binomial method.

6.1.3 Effectiveness Endpoint 3: Chronic Closure

Chronic closure is defined as the absence of a residual shunt ≥3 mm at 6 months or later.

6.1.3.1 Analysis Methods

The proportion of subjects who have chronic closure at a follow-up visit 6 months or later (from the time of first successful implant), as determined by the echocardiography core laboratory, will be estimated.

The 95% confidence interval for the rate of chronic closure will be calculated using the exact binomial method.

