4.4 Study Population

The intended population for the Amplatzer™ PIVSD Occluder is patients with post-myocardial infarct muscular VSD who are not satisfactory surgical candidates. The study will enroll subjects in two cohorts:

Cohort 1: All available Emergency and Compassionate PIVSD Occluder subject data from 2011 until the end of 2016 will be utilized to determine technical success, acute survival, and chronic survival. All subjects belonging to this cohort must have undergone an attempt to close a post-infarct VSD using the Amplatzer™ PIVSD Occluder.

Cohort 2: This cohort will consist of subjects over the age of 18 years who have previously been successfully implanted with the PIVSD Occluder and:

- for living subjects, the subject or subject's legally authorized representative has provided consent to participate in this study.
- the subject's post-procedure echocardiogram is evaluable and can be sent to the echocardiography core laboratory for residual shunt assessment.

Therefore, this cohort will be composed of retrospectively enrolled subjects. This cohort will be utilized to determine acute and chronic closure, and chronic survival.

5 Procedures

Approval from the Sponsor must be received prior to initiating study procedures. Baseline, procedure, post-procedure, and six month subject data will be collected retrospectively on each subject. The following sections provide a detailed description of procedures required by this CIP.

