5.1.1 Special circumstances for informed consent

A legally authorized representative may represent the subject during the informed consent process, which will be performed according to the requirements in section 5.1. The subject, if living, will also be informed about the clinical study within his/her ability to understand.

When obtaining informed consent from the subject is not possible because of the subject's medical condition, the Informed Consent of the subject's legally authorized representative will be requested.

In the event the subject has died, informed consent is not applicable. HIPAA compliance and other applicable federal, state and local laws will be reviewed by the center's IRB to determine the application of the Privacy Rule to a deceased subject's protected health information.

All other aspects of the informed consent process will be in compliance with section 5.1.

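### Chronic closure does not separate closure after surgery or a further occluder, and alive-with-closure in Cohort 2 is not assured to be recoverable

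*Combined protocol and SAP*

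**What the plan says.** The definition of chronic closure has the same wording in Section 4.2.1, Section 6.1.3 and Appendix B: "Chronic closure is defined as the absence of a residual shunt ≥3 mm at 6 months or later". Section 6.1.3.1 then estimates "The proportion of subjects who have chronic closure at a follow-up visit 6 months or later (from the time of first successful implant"), as read by the core laboratory, with an exact binomial interval. Its visible text names no denominator and does not mention further procedures.

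Only Cohort 2 supplies closure data. Section 4.4 says: "This cohort will be utilized to determine acute and chronic closure, and chronic survival". Entry requires a successful implant, consent if the subject is living, and that "the subject's post-procedure echocardiogram is evaluable and can be sent to the echocardiography core laboratory for residual shunt assessment". For deceased subjects, Section 5.1.1 says: "In the event the subject has died, informed consent is not applicable". Table 2 (Section 5.4) puts the late echo under the column "6 MONTHS* (>150 DAYS"), with the footnote "If subject was alive during the visit window".

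Chronic survival is a separate Kaplan-Meier endpoint at 183 days (Sections 6.1.5 and 6.1.5.1). Cohort 1 data also "will be utilized to determine technical success, acute survival, and chronic survival" (Section 4.4), and Section 5.1 lets Emergency and Compassionate Use patients enter Cohort 2. Section 6.1.5.1 does not say whether survival is pooled or shown by cohort.

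Section 5.3.2 collects the date of each procedure if there was more than one, and the models implanted. Section 5.3.3 collects implant status. Other cardiac procedures appear only as baseline history (Section 5.3.1). Surgical repair after implant is not a listed item, and the CRF is not public.

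**The concern.** The study is meant to inform safety and probable benefit of the occluder (Section 4.2). Two questions follow naturally: how many closed defects were closed by the device, and how many Cohort 2 subjects were alive with a closed defect.

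On the first, a definition based on residual shunt alone treats a surgical patch, a second occluder and a single successful implant alike. A high closure rate could therefore partly reflect rescue of incomplete closure.

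On the second, a subject who dies before the late echo has no reading and drops out of the closure rate. The death appears under survival, but possibly in an estimate that mixes in Cohort 1. Survivors without a late echo may have better or worse closure than those imaged, so the direction of any error is not known.

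**Working it through.** The visible text gives no sample size, expected rate or precision target, so there is no plan figure to reproduce. **Every count below is an assumption.** Cohort 2 is set at N = 40 with about 85% closure in those imaged. Deaths are set at 8 and 22, because 0.19 × 40 = 7.6 and 0.54 × 40 = 21.6. The 19% and 54% are the operative mortality limits for surgery in Section 2 and are not device data. A low case has 2 deaths. Intervals are exact (Clopper-Pearson) 95%.

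**1. Closure after reintervention.** Take 12 closed of 14 imaged, where one closure followed surgery and one followed a second occluder.
- As defined: 12/14 = 86%.
- Surgery not counted: 11/14 = 79% (49 to 95%).
- Second occluder also not counted: 10/14 = 71% (42 to 92%).
- With no reinterventions the three agree.

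**2. Imaged survivors against all of Cohort 2.** Let D = deaths before a late echo, A = N − D survivors, E = survivors imaged, C = closed. Conditional rate = C/E. Alive with closure lies between C/N (no unimaged survivor closed) and (C + A − E)/N (all closed).

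| D | A | E | C | C/E (95% CI) | Alive with closure |
|---|---|---|---|---|---|
| 2 | 38 | 36 | 31 | 86% (71 to 95%) | 31/40 to 33/40 = 78 to 83% |
| 8 | 32 | 24 | 20 | 83% (63 to 95%) | 20/40 to 28/40 = 50 to 70% |
| 22 | 18 | 14 | 12 | 86% (57 to 98%) | 12/40 to 16/40 = 30 to 40% |

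The assumed share of survivors without an echo is (A − E)/A: 2/38 = 5%, 8/32 = 25% and 4/18 = 22%. These shares set the width of the last column.

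**3. When survival × closure gives the joint figure.**
- Cohort 2 survival shown alone, all survivors imaged: 32/40 × 27/32 = 27/40 = 68%. This is exact.
- Cohort 2 survival alone, 24 of 32 imaged and 20 closed: 32/40 × 20/24 = 67%. This holds only if echoes are missing at random; the bounds are 50 to 70%.
- Survival pooled with a separate Cohort 1 of 40 with 22 deaths: (32 + 18)/80 = 62.5%, and 62.5% × 27/32 = 53%, against 68% for Cohort 2. If the two cohorts survive equally, this error is zero.

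**4. Time cuts.** Table 2 accepts echoes after day 150, the definition requires 6 months or later, and survival is cut at 183 days, a spread of 183 − 150 = 33 days. An echo on day 160 fits the collection window but not the definition. If it were counted and the subject died on day 170, that subject would be a closure success and a survival failure, and the product in step 3 would no longer be exact.

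**5. Bias in the companion figure.** Consent is needed only from living subjects, so deaths may be over-represented. Suppose every survivor is imaged and 10 eligible living subjects with the same closure rate stay out for lack of consent.
- With 8 deaths: 27/40 = 68% observed, against (27 + 10 × 27/32)/50 = 71%.
- With 22 deaths: 15/40 = 38% observed, against (15 + 10 × 15/18)/50 = 47%.

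**The case against.** The strongest reply is that the public text is visibly cut. Section numbers jump from 6.1.5.1 to 6.4, and 6.1.2.1 and 6.1.4.1 have lost opening characters or words. A denominator, a missing-echo rule or a by-cohort rule may sit there. This stands, so that part is a request to confirm. It has less force for the closure definition, which appears in full three times, and for the time cuts, which are all visible.

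Four stronger readings are tempting, and the documents do not support them.
- A reader might infer that a survivor-only rate is invalid or hides deaths. It is a legitimate conditional rate, deaths have their own endpoint, and Section 6.1 tests no hypotheses.
- A reader might infer that alive-with-closure cannot be obtained. Step 3 shows that it can, exactly, if Cohort 2 survival is shown alone, echoes are complete and the time cuts agree. Pooling is a possibility; no section states it.
- A reader might infer that closure is formally credited to the first implant. Section 6.1.3.1 uses that implant only as the time origin. Repeat procedures are recorded if they occurred, and may include failed attempts before the first success. A second PIVSD Occluder is still the device under study.
- A reader might infer the number lacking the endpoint from the enrolment of deceased subjects. Someone deceased at enrolment may have had a late echo first.

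It is also fair to say that the illustrative counts are not evidence of size, and that an alive-with-closure figure is supplementary.

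**Conclusion.** The point holds as a gap in definition and reporting. Most securely, the shunt-only definition does not distinguish closure after surgery or a further occluder, and the three time cuts do not agree. Less securely, because the denominator is inferred from the Table 2 footnote and text is missing, recovery of alive-with-closure for Cohort 2 is not assured.

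The true size cannot be derived: no Cohort 2 size, deaths, late-echo counts or reintervention counts are visible. Under the assumptions above, the gap between the imaged-survivor rate and alive-with-closure runs from 3 to 8 percentage points (2 deaths) to 46 to 56 points (22 deaths). The reintervention effect runs from none to 14 points. This is a worthwhile, inexpensive improvement and does not undermine the design.

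**What to change.** In Section 6.1.3.1:

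1. Do not count closure after surgical repair or explant as device closure. Show closure with and without a further occluder, using the dates, models and implant status already collected. Add a record-abstracted surgical-repair item if the CRF lacks one.
2. Reconcile Table 2 with the endpoint definition, and state how the chosen cut relates to 183 days.
3. Label the current rate as closure among survivors with an evaluable late echo. Add a Cohort 2 table: alive and closed, alive and not closed, alive without echo, dead, unknown. Give a supplementary alive-with-closure proportion with exact interval and best- and worst-case bounds for missing echoes. State that it is conditional on Cohort 2 entry and is not a rate per implanted patient.
4. Show Cohort 2 chronic survival separately from Cohort 1.

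If removed text already holds a denominator or missing-echo rule, a cross-reference is enough for that part.

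The cost is SAP wording, one table, possibly one CRF field filled from records, and the amendment notification described in Appendix A. No new patient contact is needed. The downside is a less favourable and possibly wide companion figure, which may be biased downward as in step 5.

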6.1.4 Safety Endpoint 1: Acute Survival

[figure not shown]
Acute survival is defined as survival for at least 24 hours following an attempted PIVSD device implant.

Template: 86357 Rev. F Page 13 of 26

Clinical Investigation Plan

6.1.4.1 Analysis Methods

confidence interval for the rate of acute survival will be calculated using the exact binomial method.

6.1.5 Safety Endpoint 2: Chronic Survival

Chronic survival is defined as survival for at least 183 days from the time of first successful implant.

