4.1 Clinical Study Design

This is a multi-center, observational study to evaluate the safety and probable benefit of the Amplatzer™ PIVSD Occluder for use in transcatheter closure of muscular ventricular septal defects following a myocardial infarction in the post approval setting.

As described in section 4.2, this study has five endpoints (safety: acute and chronic survival; effectiveness: technical success, acute and chronic closure). Two cohorts will be utilized to obtain study endpoint data. Cohort 1 will be comprised of all available Emergency and Compassionate PIVSD Occluder subject data from 2011 until the end of 2016 and these data will be used to determine technical success, acute survival, and chronic survival.

Template: 86357 Rev. F Page 6 of 26

Clinical Investigation Plan

[figure not shown]
[figure not shown]

Table 1: Estimated Timeline of Milestone Events

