4.2.2 Safety Endpoints

Acute Survival: Acute survival is defined as survival for at least 24 hours following an attempted PIVSD device implant.

Chronic Survival: Chronic survival is defined as survival for at least 183 days post-procedure.

Template: 86357 Rev. F Page 7 of 26

Clinical Investigation Plan

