5.3 Procedures

For Cohort 1, all available Emergency and Compassionate PIVSD Occluder subject data from 2011 until the end of 2016 will be utilized to determine technical success, acute survival, and chronic survival. Any available demographic/medical history information implant success and survival within 24 hours of the procedure and through 183 days post-procedure will be documented. No additional information will be collected in this cohort.

The Principal Investigator is responsible for ensuring all clinical study data is collected as required per CIP scheduled procedures.

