5.3.2 Implant/Procedure and Post-Procedure

The following procedure information will be collected retrospectively via each subject's medical records:

- Date of procedure (if multiple procedures occurred, date of each procedure)
- Procedure success in a subject
- Implanted device(s) model number(s)
- Post-procedure echocardiogram obtained immediately after the successful deployment of the device and up to 7 days post-procedure is evaluable and can be sent to the echocardiography core laboratory for residual shunt evaluation.

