6.1.5.1 Analysis Methods

The probability of a subject who is alive for at least 183 days will be estimated by the Kaplan-Meier method. Subjects whose survival status is not known for at least 183 days post-procedure (first successful implant) will be censored on the date at which survival status was known. The day of procedure will be considered Day 0 when referring to a specific number of days for the Kaplan-Meier analysis. The 95% confidence interval for the rate of chronic survival will be calculated using Greenwood's formula for the variance of the Kaplan-Meier estimator.

Template: 86357 Rev. F Page 14 of 26

Clinical Investigation Plan

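### Chronic survival is counted from first successful implant, which gives attempted but never-implanted Cohort 1 subjects no Day 0, and no visible sentence says whether they are counted

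*Combined protocol and SAP*

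**What the plan says.** **Definition of the endpoint.** Section 4.2.2: "Chronic survival is defined as survival for at least 183 days post-procedure". Section 6.1.5, repeated in Appendix B: "Chronic survival is defined as survival for at least 183 days from the time of first successful implant".

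**Analysis.** Section 6.1.5.1 uses Kaplan-Meier with a Greenwood interval. Its censoring rule equates the two origins: "Subjects whose survival status is not known for at least 183 days post-procedure (first successful implant) will be censored". The next sentence carries no such qualifier: "The day of procedure will be considered Day 0 when referring to a specific number of days for the Kaplan-Meier analysis".

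**Who supplies the data.** Section 4.1 says of Cohort 1 that "these data will be used to determine technical success, acute survival, and chronic survival". Section 4.4 sets its entry criterion: "All subjects belonging to this cohort must have undergone an attempt to close a post-infarct VSD". A successful implant is not required. Section 5.3 says that for this cohort "survival within 24 hours of the procedure and through 183 days post-procedure will be documented". Cohort 2 also supplies chronic survival, but Section 4.4 limits it to successfully implanted subjects.

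**The other safety endpoint.** Section 6.1.4 counts acute survival over 24 hours from an attempted implant, so it covers failed attempts.

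**The concern.** Technical success is itself estimated in Cohort 1, so the plan allows for failed attempts. A subject whose attempt failed, and who never received a device later, has a procedure date but no date of first successful implant. Read literally, Section 6.1.5 gives that subject no time zero. An analyst following 6.1.5 could therefore leave the subject out, while an analyst following 4.2.2 and 5.3 would keep the subject in. The two would report different Cohort 1 figures from the same data.

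If such subjects are left out, the two safety endpoints describe different people: all attempts for acute survival, implanted subjects only for chronic survival. A never-implanted subject who dies on day 5, say, is an acute survivor and is absent from chronic survival, so neither safety endpoint records the death. Section 6.6.2 says that no adverse events are collected, so survival is the only safety information the study produces. Section 6.1 states that no hypotheses are tested, so no pass/fail result is at risk. What is at risk is the meaning of a safety estimate.

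**Working it through.** **Step 1. The two origins, by type of subject.**

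| Subject | From procedure (4.2.2) | From first successful implant (6.1.5, Appendix B) |
|---|---|---|
| Implanted at the only procedure (either cohort) | That day | The same day |
| Failed attempt, later success | First or later procedure; 4.2.2 does not say | Day of the success |
| Attempted, never implanted (Cohort 1 only) | Day of the attempt | Undefined |

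The first row raises no issue. In the second, the parenthesis in 6.1.5.1 points to the day of success. In the third it cannot help, because there is no implant to date from.

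**Step 2. How much the second row could matter.** Let success come d days after the first attempt and death T days after the first attempt. The 183-day status differs between the origins only if 183 < T ≤ 183 + d. That is a narrow window.

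**Step 3. How much the third row could matter.** The visible text gives no sample size, technical success rate or survival rate for this device, so there is no plan figure to reproduce. Ignoring censoring:

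- All-attempt survival = TS × S_imp + (1 − TS) × S_fail
- Implanted-only minus all-attempt = (1 − TS) × (S_imp − S_fail)

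TS is technical success, S_imp is 183-day survival if implanted and S_fail is 183-day survival if never implanted. All three are assumed below. For S_fail, the 10% and 83% values are 1 minus the Section 2 mortality figures for medical therapy (over 90%, so 10% is an upper value) and mechanical support (about 17%). They are weak proxies: neither is stated at 183 days, and neither describes care after a failed closure attempt. The 0% value is the logical floor.

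| TS | S_imp | S_fail | Difference (points) |
|---|---|---|---|
| 0.80 | 0.60 | 0.10 | 0.20 × 0.50 = +10.0 |
| 0.80 | 0.60 | 0.83 | 0.20 × (−0.23) = −4.6 |
| 0.70 | 0.60 | 0.00 | 0.30 × 0.60 = +18.0 |
| 0.70 | 0.50 | 0.83 | 0.30 × (−0.33) = −9.9 |
| 0.95 | 0.60 | 0.00 | 0.05 × 0.60 = +3.0 |
| 0.95 | 0.50 | 0.83 | 0.05 × (−0.33) = −1.65 |

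The sign is positive if never-implanted subjects survive less well than implanted ones, and it reverses if they survive better.

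**Step 4. An example in counts (assumed).** Take 50 attempted and 40 implanted, with 20 of 40 implanted and 1 of 10 never-implanted subjects alive at 183 days, and no censoring. The Greenwood standard error then reduces to √(p(1 − p)/n).

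- Implanted only: 20/40 = 50.0% (95% CI 34.5 to 65.5)
- All attempted: 21/50 = 42.0% (95% CI 28.3 to 55.7)

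The 8-point gap comes from the choice of population, not from sampling.

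**Step 5. Pooling.** The visible text does not say whether the cohorts are combined for this endpoint. If they were, (1 − TS) would be replaced by the never-implanted share of everyone analysed. That share is smaller, because Cohort 2 adds only implanted subjects.

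**The case against.** **The origin is largely settled.** Section 6.1.5, Appendix B and the parenthesis in 6.1.5.1 agree on first successful implant. The Day 0 sentence follows that parenthesis directly and reads most naturally as a day-numbering convention for the same procedure. A reader might infer that the plan has two rival time origins throughout, including for Cohort 2 and for subjects with several procedures. The documents do not support that: once a subject is implanted, the parenthesis probably identifies the starting procedure. Only the wording of 4.2.2 remains to be aligned. This objection stands for implanted subjects. It does not reach a subject who was never implanted.

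**The population rule may exist.** The visible numbering passes from 6.1.5.1 to 6.4, and 6.1.4.1 begins mid-sentence. An analysis-set statement could sit in text that is not visible, so the documents do not support saying that the plan omits one. Even if one exists, the definitions in 4.2.2 and 6.1.5 still differ.

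**The bias is not demonstrated.** A reader might infer that reported survival will be inflated, or that failed attempts are hidden. Neither is established. The direction depends on rates the documents do not give, and failed attempts do show in the technical success rate. What would not show is whether those subjects died between 24 hours and 183 days.

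**Two origins for one endpoint.** Starting Cohort 1 at the attempt and Cohort 2 at the implant could look inconsistent. Reporting the implanted-only estimate for Cohort 1 as well answers this, since that estimate has the same origin in both cohorts.

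**Conclusion.** The concern holds for attempted, never-implanted Cohort 1 subjects. The plan assigns an attempt-defined cohort to an endpoint whose stated start date those subjects do not have, and no visible sentence says how they are handled. If 6.1.5 is followed literally, they can drop out of chronic survival, and their deaths after 24 hours count in neither safety endpoint. For implanted subjects, including all of Cohort 2 and those with more than one procedure, the matter is mainly one of aligned wording.

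The size and direction cannot be taken from the documents. The Step 3 figures are illustrations that rest on assumed rates and on Cohort 1 being reported alone. The effect is small when technical success is high, nil if every attempt succeeded, and diluted if the cohorts are pooled. The conclusion also depends on no contrary rule standing in the text not visible around 6.1.4 to 6.3. It should be fixed before analysis, because it changes what a safety estimate means and costs little to settle.

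**What to change.** 1. Align Sections 4.2.2, 6.1.5, 6.1.5.1 and Appendix B so that each gives the same origin and population for each reported estimate.
2. Cohort 1: estimate 183-day survival in all attempted subjects, with Day 0 at the first attempt (Section 6.1.1 already defines an attempt). Use the recorded procedure date where a first-attempt date is unavailable.
3. Cohort 1: also report survival from first successful implant among implanted subjects. Label each estimate with its population and origin.
4. Cohort 2: keep first successful implant, the origin that Section 6.1.3.1 already uses for chronic closure.
5. Report how many Cohort 1 subjects were never implanted.

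**Cost.** Wording in four places and one extra Kaplan-Meier estimate, on survival data that Section 5.3 already plans to document. The all-attempt figure may be less favourable. Some first-attempt dates may be missing: Section 5.3.2 asks for the date of every procedure, but it is not clear that this item applies to Cohort 1, for which Section 5.3 rules out collecting anything further.
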